2.5 Objectives

The primary aim of the study is to compare the effects of three types of micronutrient supplements among Ghanaian pregnant and lactating women and to assess the effect of LNS-P&L given to pregnant and lactating women and LNS-20gM provided to children from 6 to 18 mo of age on child growth and micronutrient status. We also aimed to explore what background characteristics (e.g. social, economic, demographic, health, nutritional, etc.) might modify the effects of LNS among women and their infants.

The null hypotheses were that:

a) The three groups of infants whose mothers receive the three micronutrient treatments will not differ significantly in mean birth length (crude length and length-for-age z-score), and

b) Infants whose mothers received LNS during pregnancy and lactation, and who receive LNS from 6 to 18 months of age will not differ significantly in length-for-age z-score at 18 mo from infants of the other two groups.

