2.9 Analysis principles

- The primary analysis will be by intention-to-treat. That is, results for all women enrolled (including data on their infants) will be analyzed according to the group to which they were assigned regardless of any protocol violations. Data on subjects who were lost to follow-up because of death, travel from the study site, or refusal to continue with the study will be included in the analysis if available.
- All tests will be two-sided, at 5% level of significance.
- Where more than 10% of observations are missing for a dependent variable, we will report the number of observations used in the analysis.

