3.0 Design

3.1 Sample size and power

Sample size calculations were based on being able to detect an effect size of 0.3 (difference between groups, divided by the pooled SD) for each outcome, assuming 3 groups, power of 80% and alpha=0.05. This required 216 per group, for a total of 648 subjects. Allowing for up to 25% loss to follow-up by 18 months, we needed to recruit 864 subjects. For the biochemical outcomes, we assumed an effect size of at least 0.5, which required a subsample of 79 per group, for a total of 315 subjects after allowing for attrition.

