4.8 Analysis of the effect of the intervention

The analysis of the effect of the intervention (at single time points or repeated measures) will begin with testing the null hypothesis of no difference among the three treatment groups using ANCOVA or logistic regression, and controlling for pre-specified covariates including, in the case of women, baseline values. Because infants will not have true baseline values unaffected by intervention, most of the covariates used in analyses involving infants will be mothers' baseline characteristics. Only covariates significantly associated with an outcome at 10% level of significance in a bivariate analysis will be include in the final adjusted analysis. This means we may have different sets of covariates for each outcome.

For all analyses, if the global null hypothesis is rejected at 0.05 level, then we will perform post-hoc pairwise comparisons of all three groups using Tukey-Kramer adjustment (for continuous variables) or the "Contrast" statements (for categorical variables) in SAS. We will also use Scheffe's test to assess whether the LNS group differs from the non-LNS groups with respect to most outcomes, and whether the IFA group differs from the non-IFA groups with respect to iron outcomes or variables such as morbidity which might be affected by iron status.

The effects of potential effect modifiers will be assessed with an interaction term in the ANCOVA or logistic regression model. Significant interactions (p < 0.05) will be further examined with stratified analyses, estimation of separate regression lines, or estimation of adjusted means at key points of the covariate, in order to understand the nature of the effect modification.

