4.9 Comparison of primary outcomes at birth and 18 months of age

The ANCOVA to determine the effects of the intervention on birth length (crude length and length-for-age z-score) and length-for-age z-score at 18 mo among the three intervention groups will be performed using PROC GLM. Results will be summarized as mean and SD and tabulated, by group (**Table 2** and **Table 3**).

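### The 18-month hypothesis sets LNS against the other two groups, but the only test named for that comparison is Scheffe's, which costs 7.5 points of power at the design effect

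*SAP*

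**What the plan says.** SAP section 2.5 words its two null hypotheses differently. Null (a), on birth length, is that the three groups do not differ. Null (b) is that infants in the LNS arm "will not differ significantly in length-for-age z-score at 18 mo from infants of the other two groups". IFA against MMN is not part of (b), and section 2.1 gives neither of those groups an infant supplement.

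The analysis is the same for both primary outcomes. Section 4.9 says that the ANCOVA for "length-for-age z-score at 18 mo among the three intervention groups will be performed using PROC GLM", and it names no contrast. Section 4.8 starts from a global test of the three groups, follows a rejection with Tukey-Kramer comparisons of all pairs, and adds: "We will also use Scheffe's test to assess whether the LNS group differs from the non-LNS groups with respect to most outcomes".

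Section 2.9 sets the level: "All tests will be two-sided, at 5% level of significance". Section 3.1 sizes the trial to "detect an effect size of 0.3 (difference between groups, divided by the pooled SD) for each outcome". With three arms, a target of 80% power and the 5% level, its stated result is: "This required 216 per group, for a total of 648 subjects".

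**The concern.** Hypothesis (b) singles out one arm before any results are known, and section 4.8 itself phrases the comparison as LNS against the non-LNS groups. Neither test that the plan offers for it fits well. The global F test has two degrees of freedom, one of which goes to IFA against MMN. Scheffe's test uses a critical value that protects every contrast one could form from three means. For a single contrast written down beforehand, an ordinary two-sided t test in the ANCOVA already holds 5%.

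At stake is the chance of detecting a real LNS effect on the second primary outcome. There is also a band of observed differences in which the choice of test alone decides whether LNS is declared different from the other groups.

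**Working it through.** **Inputs.** From SAP section 3.1: effect 0.30 SD, three groups, 80% power, alpha 0.05, 216 evaluable per group, 25% loss. From section 2.9: two-sided 5%. Assumptions of this check: equal groups, SD = 1 on the standardised scale, no precision gained from covariates, and IFA = MMN unless stated otherwise.

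**The plan's own figure.** Take a global F test with the extreme groups 0.30 SD apart and the third midway. The noncentrality is n × 0.30²/2. At n = 216 this is 9.72, with power 80.2%, and 216 is the smallest n that reaches 80%. Then 3 × 216 = 648 and 648/0.75 = 864, which matches "Allowing for up to 25% loss to follow-up by 18 months, we needed to recruit 864 subjects". The sample size therefore corresponds to the two-degree-of-freedom test.

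**The contrast.** Let d be the LNS mean minus the average of the IFA and MMN means.
- Standard error: √(1/216 + 1/432) = √(1.5/216) = 1/12 SD.
- Noncentrality of t: 12d, with 648 − 3 = 645 degrees of freedom.
- Critical |t| for a planned contrast: t(0.975; 645) = 1.964.
- Critical |t| for Scheffe: √(2 × F(0.95; 2, 645)) = 2.453.
- Global F: noncentrality (12d)², which is 12.96 at d = 0.30.

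**Power, with IFA = MMN:**

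| d (SD) | Planned contrast | Global F | Scheffe | Scheffe loss (points) |
|---|---|---|---|---|
| 0.35 | 98.7% | 97.1% | 95.9% | 2.8 |
| 0.30 | 94.9% | 90.6% | 87.4% | 7.5 |
| 0.25 | 85.0% | 76.9% | 70.8% | 14.2 |
| 0.20 | 66.9% | 56.4% | 47.9% | 19.0 |
| 0.18 | 57.8% | 47.3% | 38.5% | 19.3 |

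The Scheffe loss peaks at 19.3 points near d = 0.18. The global F loses at most 10.6 points.

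**Other ways to see the size.**
- Smallest effect detectable with 80% power: (1.964 + 0.842)/12 = 0.234 SD for the planned contrast, and (2.453 + 0.842)/12 = 0.275 SD for Scheffe.
- Equivalent sample size: (3.295/2.806)² = 1.38, so 38% more children. For 80% power at 0.30 SD, the planned contrast needs 132 per group and Scheffe 182. Both are below 216.
- Band in which the tests disagree: observed differences from 1.964/12 = 0.164 to 2.453/12 = 0.204 SD are significant by the planned contrast but not by Scheffe.
- Type I error for this one contrast under Scheffe: 1.4%, against the 5% in section 2.9.

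**Does requiring a significant global test first add to the loss?** For Scheffe it does not, because a significant Scheffe contrast implies a significant F. In simulation (400,000 replicates) power at 0.30 SD was 87.4% with and without that requirement. For the planned contrast it would matter: power falls from 94.9% to 90.2% if a significant F is required first.

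**If MMN lies midway (0, 0.15, 0.30).** Now d = 0.30 − 0.075 = 0.225. Power is 80.2% for the global F, 76.9% for the planned contrast and 59.8% for Scheffe.

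**If LNS = MMN and both exceed IFA by 0.30 SD.** Now d = 0.30 − 0.15 = 0.15. The pooled contrast rejects about 43.5% of the time although LNS adds nothing over MMN.

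**The case against.** The strongest reply is that the SAP never makes Scheffe decisive for this outcome. Section 4.9 specifies the three-group ANCOVA, Table 3 gives the 18-month z-score a single P-value labelled ANCOVA, and Scheffe is something the authors will also use for most outcomes. This stands. A reader might infer that the primary result hangs on Scheffe, but the text does not say so. Measured against the global F, a planned contrast gains 4.3 points at 0.30 SD (94.9% against 90.6%).

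Second, section 2.5 does not say that the other two groups are pooled. It can also be read as LNS against IFA and LNS against MMN, for which Tukey-Kramer is planned, and Table 4 sets out separate odds ratios for IFA and MMN. The pooled form is thus a reading, supported by the LNS and non-LNS wording of section 4.8. The pairwise reading would not make the plan a close fit either. Tukey-Kramer adjusts for three pairs, one of which is outside (b), and its power per pair at 0.30 SD is 77.9%.

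Third, the gain assumes IFA = MMN, which the SAP does not state. MMN mothers receive multiple micronutrients through pregnancy and six months postpartum, and IFA mothers do not. With MMN midway, the pooled contrast falls below the global F. It can also reject because IFA alone is low. Both points stand and shape the fix.

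Fourth, Scheffe errs on the conservative side and protects a family of comparisons. It is true that no false-positive risk arises. But hypothesis (b), read as one contrast, does not need protection for a whole family.

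**Conclusion.** The concern holds as a matter of efficiency. For the one comparison that hypothesis (b) fixes in advance, the only named test carries an unnecessary penalty. It costs 7.5 points of power at the SAP's own effect size (94.9% to 87.4%), given 216 per group, IFA = MMN and no covariate gain.

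Three stronger readings are tempting but unsupported:
- **That the trial is underpowered.** At 0.30 SD with IFA = MMN, Scheffe keeps 87.4%, above the 80% target.
- **That the loss is typically near 19 points.** That figure needs a true effect near 0.2 SD, which section 3.1 does not assume.
- **That the global test and Scheffe penalise twice.** They do not: the loss from using Scheffe is Scheffe's alone.

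This is a cheap improvement and not a must-fix. It concerns hypothesis (b) only. It gives no ground for replacing Scheffe with unadjusted IFA against non-IFA contrasts for the secondary iron and morbidity outcomes.

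**What to change.** In sections 4.8 and 4.9, state that hypothesis (b) is tested by one pre-specified contrast in the ANCOVA for 18-month length-for-age z-score: LNS minus the mean of IFA and MMN, two-sided 5%, reported as an adjusted difference with its 95% confidence interval. It should replace Scheffe for this comparison and should not wait on a significant global test.

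Keep the three-group test. Report the Tukey-Kramer LNS-IFA and LNS-MMN differences beside the contrast whatever the global result, so that a pooled difference driven by a low IFA mean is not read as LNS being better than MMN.

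The cost is a few lines of SAP text and one SAS statement, with no new data. The statistical price should be stated openly: if MMN lies midway between IFA and LNS, the pooled contrast has about 77% power against about 80% for the global F, though still more than Scheffe's 60%. The change should be made before the group assignments are released to the investigators.

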4.9 Comparison of primary outcomes at birth and 18 months of age

The ANCOVA to determine the effects of the intervention on birth length (crude length and length-for-age z-score) and length-for-age z-score at 18 mo among the three intervention groups will be performed using PROC GLM. Results will be summarized as mean and SD and tabulated, by group (**Table 2** and **Table 3**).

4.10 Comparison of secondary outcomes

i. Comparison at single time points

Comparison of secondary outcomes at single time points will be performed using PROC GLM (for continuous outcome variables), and PROC FREQ and PROC LOGISTIC for categorical outcome variables. Continuous variables will be summarized using either mean and SD, or median and range. Categorical variables will be summarized using percentages and Odds Ratios, with 95% Confidence Intervals (95% CI).

Analysis of several secondary outcomes at birth and 18 months of age will be presented alongside the primary outcomes in **Table 2** and **Table 3** as well as in **Table 4**. Prior to the analysis of additional secondary outcomes at other single time points, this SAP will be updated to include those specific single time points, and how results will be presented.

ii. Comparison of repeated measures

For continuous outcome variables, a linear mixed model (PROC MIXED) will be used to compare patterns in the outcome variables across time among the groups. For categorical variables, a variant mixed model logistic regression (SAS PROC GLIMMIX) will be used. Prior to analysis of repeated measures, this SAP will be updated to include the specific analyses and the presentation of the results.

4.11 Selection of covariates and effect modifiers in the analysis of primary outcomesBelow we list the two primary outcomes to be analyzed (both at single time points), and indicate the covariates and effect modifiers that will be used for each analysis. Each of the effect modifiers will be considered separately in the regression model to avoid collinearity.

Primary	Analysis	Covariates	Effect modifiers
outcome			
variable			
Birth length	ANCOVA	- Maternal height	- Maternal height
(crude	(SAS Proc	- Maternal BMI	- Maternal BMI
length in cm	glm)	- Gestational age at enrolment	- Gestational age at enrollment
and length-		- Maternal age	- Maternal age
for-age z-		- Child sex	- Child sex
score)		- Maternal education	- Maternal education
		- Proxy for SES	- Proxy for SES
		- Parity	- Parity
		- Season at enrolment	- Season at enrolment
		- Mother's marital status	- Maternal anemia at enrollment
Length-for-	ANCOVA	- Maternal height	- Maternal height
age z-score	(SAS Proc	- Maternal BMI	- Maternal BMI
at 18 months	glm)	- Gestational age at enrolment	- Gestational age at enrollment
		- Maternal age	- Maternal age
		- Child sex	- Child sex
		- Maternal education	- Maternal education
		- Proxy for SES	- Proxy for SES
		- Parity	- Parity
		- Season at enrolment	- Season at enrolment

Covariates	Effect modifiers
- Mother's marital status	- Maternal anemia at enrollment
	- Mother's marital status

4.12 Selection of covariates and effect modifiers in the analysis of secondary outcomes Prior to analyses for secondary outcomes, this SAP will be updated with an *a priori* list of covariates and effect modifiers, as has been done for the primary outcomes above.

4.13 Data transformation

Based on previous studies, we expect the primary outcome variables (birth length – crude length in cm and length-for-age z-score – measured within 48 hours of delivery and length-for-age z-score at 18 months of age) to be normally distributed. Continuous outcomes will be assessed for conformance to the normal distribution and will be transformed appropriately. If no suitable transformation can be found to optimize normality and homogeneity of variances, analysis will be done on ranked data. Also see section 4.3 (Outliers).

4.14 Confidence intervals

Estimates of treatment effects will be accompanied by a 95 % confidence interval, wherever possible.

Tables

Table 1aBaseline characteristics of women who completed the study

Variable	IFA $(\bar{x} \pm SD)[n]$	$\frac{\mathbf{MMN}}{(\bar{x} \pm \mathbf{SD})[\mathbf{n}]}$	LNS $(\bar{x} \pm SD) [n]$	P- value	Test
Number of participants	X.X	X.X	X.X		
Age, y	$x.x \pm x.x [x]$	$x.x \pm x.x [x]$	$x.x \pm x.x [x]$	x.xx	ANOVA
Years of formal education	$x.x \pm x.x [x]$	$x.x \pm x.x [x]$	$x.x \pm x.x [x]$	x.xx	ANOVA
Marital status (% [n])	x.x [x]	x.x [x]	x.x [x]	X.XX	Chisq
Proxy for socioeconomic status	$x.x \pm x.x [x]$	$x.x \pm x.x [x]$	$x.x \pm x.x [x]$	X.XX	ANOVA
Parity	$x.x \pm x.x [x]$	$x.x \pm x.x [x]$	$x.x \pm x.x [x]$	X.XX	ANOVA
Weight (kg)	$x.x \pm x.x [x]$	$x.x \pm x.x [x]$	$x.x \pm x.x [x]$	X.XX	ANOVA
Height (m)	$x.x \pm x.x [x]$	$x.x \pm x.x [x]$	$x.x \pm x.x [x]$	X.XX	ANOVA
BMI (kg/m ²)	$x.x \pm x.x [x]$	$x.x \pm x.x [x]$	$x.x \pm x.x [x]$	X.XX	ANOVA
Mid upper arm circumf. (cm)	$x.x \pm x.x [x]$	$x.x \pm x.x [x]$	$x.x \pm x.x [x]$	X.XX	ANOVA
Triceps skinfold (cm)	$x.x \pm x.x [x]$	$x.x \pm x.x [x]$	$x.x \pm x.x [x]$	X.XX	ANOVA
Gestational age at enrolment	$x.x \pm x.x [x]$	$x.x \pm x.x [x]$	$x.x \pm x.x [x]$	X.XX	ANOVA
Hemoglobin	$x.x \pm x.x [x]$	$x.x \pm x.x [x]$	$x.x \pm x.x [x]$	X.XX	ANOVA
Positive rapid test for malaria (%)	x.x [x]	x.x [x]	x.x [x]	X.XX	Chisq
Elevated Acute phase response (%)	x.x [x]	x.x [x]	x.x [x]	X.XX	Chisq
ZPP	$x.x \pm x.x [x]$	$x.x \pm x.x [x]$	$x.x \pm x.x [x]$	X.XX	ANOVA
TfR	$x.x \pm x.x [x]$	$x.x \pm x.x [x]$	$x.x \pm x.x [x]$	X.XX	ANOVA
Ferritin (geometric mean)	$x.x \pm x.x [x]$	$x.x \pm x.x [x]$	$x.x \pm x.x [x]$	X.XX	ANOVA
Anemia (%)	xxx/ xxx (xx)	xxx/ xxx (xx)	xxx/ xxx (xx)	X.XX	Chisq
Plasma lipid profile	$x.x \pm x.x [x]$	$x.x \pm x.x [x]$	$x.x \pm x.x [x]$	X.XX	Chisq

Table 1bBaseline characteristics of infants who completed the study

Variable	IFA	MMN	LNS	P-	Test
	$(\bar{x} \pm SD) [n]$	$(\bar{x} \pm SD)[n]$	$(\bar{x} \pm SD)[n]$	value	
Number of participants	x.x	X.X	X.X		
Mother's education (y)	$x.x \pm x.x [x]$	$x.x \pm x.x [x]$	$x.x \pm x.x [x]$	x.xx	ANOVA
Mother's marital status (% [n])	x.x [x]	x.x [x]	x.x [x]	x.xx	Chisq
Number of persons in the household	x.x ± x.x [x]	$x.x \pm x.x [x]$	$x.x \pm x.x [x]$		Kruskal Wallis
Children <5 y in the household	x.x ± x.x [x]	$x.x \pm x.x [x]$	$x.x \pm x.x [x]$		Kruskal Wallis
Proxy household socioeconomic status	$x.x \pm x.x [x]$	$x.x \pm x.x [x]$	$x.x \pm x.x [x]$	x.xx	ANOVA
Parity	$x.x \pm x.x [x]$	$x.x \pm x.x [x]$	$x.x \pm x.x [x]$	x.xx	ANOVA
Mother's weight (kg)	$x.x \pm x.x [x]$	$x.x \pm x.x [x]$	$x.x \pm x.x [x]$	x.xx	ANOVA
Mother's height (m)	$x.x \pm x.x [x]$	$x.x \pm x.x [x]$	$x.x \pm x.x [x]$	x.xx	ANOVA
Mother's BMI (kg/m ²)	$x.x \pm x.x [x]$	$x.x \pm x.x [x]$	$x.x \pm x.x [x]$	x.xx	ANOVA
Mother's mid upper arm circumf. (cm)	$x.x \pm x.x [x]$	$x.x \pm x.x [x]$	$x.x \pm x.x [x]$	x.xx	ANOVA
Mother's triceps skinfold (cm)	$x.x \pm x.x [x]$	$x.x \pm x.x [x]$	$x.x \pm x.x [x]$	X.XX	ANOVA
Mother's gestational age at enrolment	$x.x \pm x.x [x]$	$x.x \pm x.x [x]$	$x.x \pm x.x [x]$	x.xx	ANOVA

Table 2
Indices of pregnancy outcome, by group

Variable	IFA	MMN	LNS	P-	Test
	$(\bar{x} \pm SD)[n]$	$(\bar{x} \pm SD)[n]$	$(\bar{x} \pm SD)[n]$	value	
Gestational age delivery (wk)	$x.x \pm x.x [x]$				ANCOVA
		$x.x \pm x.x [x]$	$x.x \pm x.x [x]$		
Birth weight (kg)	$x.x \pm x.x [x]$	$x.x \pm x.x [x]$	$x.x \pm x.x [x]$	x.xx	ANCOVA
Birth length (cm)	$x.x \pm x.x [x]$	$x.x \pm x.x [x]$	$x.x \pm x.x [x]$	x.xx	ANCOVA
Head Circumference at birth (cm)	$x.x \pm x.x [x]$	$x.x \pm x.x [x]$	$x.x \pm x.x [x]$	x.xx	ANCOVA
MUAC at birth (cm)	$x.x \pm x.x [x]$	$x.x \pm x.x [x]$	$x.x \pm x.x [x]$	X.XX	ANCOVA
Weight-for-age z-score	$x.x \pm x.x [x]$	$x.x \pm x.x [x]$	$x.x \pm x.x [x]$	x.xx	ANCOVA
Length-for-age z-score	$x.x \pm x.x [x]$	$x.x \pm x.x [x]$	$x.x \pm x.x [x]$	x.xx	ANCOVA
Weight-for-length z-score	$x.x \pm x.x [x]$	$x.x \pm x.x [x]$	$x.x \pm x.x [x]$	x.xx	ANCOVA
Head circumffor-age z-score	$x.x \pm x.x [x]$	$x.x \pm x.x [x]$	$x.x \pm x.x [x]$	X.XX	ANCOVA
Low birth weight (% (95% CI))	x.x (x.x - x.x)	x.x (x.x - x.x)	x.x (x.x - x.x)	X.XX	FREQ
Premature delivery (% (95% CI))	x.x (x.x - x.x)	x.x (x.x - x.x)	x.x (x.x - x.x)	X.XX	FREQ

Table 3Comparison of anthropometric status in the intervention groups at 18 months

Variable	IFA	MMN	LNS	P-	Test
	$(\bar{x} \pm SD) [n]$	$(\bar{x} \pm SD)[n]$	$(\bar{x} \pm SD)[n]$	value	
Weight (kg)	$x.x \pm x.x [x]$	$x.x \pm x.x [x]$	$x.x \pm x.x [x]$	x.xx	ANCOVA
Length (cm)	$x.x \pm x.x [x]$	$x.x \pm x.x [x]$	$x.x \pm x.x [x]$	x.xx	ANCOVA
MUAC (cm)	$x.x \pm x.x [x]$	$x.x \pm x.x [x]$	$x.x \pm x.x [x]$	X.XX	ANCOVA
Head circumference (cm)	$x.x \pm x.x [x]$	$x.x \pm x.x [x]$	$x.x \pm x.x [x]$	x.xx	ANCOVA
Weight-for-age z-score (SD)	$x.x \pm x.x [x]$	$x.x \pm x.x [x]$	$x.x \pm x.x [x]$	x.xx	ANCOVA
Length-for-age z-score (SD)	$x.x \pm x.x [x]$	$x.x \pm x.x [x]$	$x.x \pm x.x [x]$	x.xx	ANCOVA
Weight-for-length z-score (SD)	$x.x \pm x.x [x]$	$x.x \pm x.x [x]$	$x.x \pm x.x [x]$	x.xx	ANCOVA
Head circumference-for-age z-score	$x.x \pm x.x [x]$	$x.x \pm x.x [x]$	$x.x \pm x.x [x]$	x.xx	ANCOVA
Arm circumference-for-age z-score	$x.x \pm x.x [x]$	$x.x \pm x.x [x]$	$x.x \pm x.x [x]$	x.xx	ANCOVA

Table 4Prevalence of malnutrition at 18 months of age and adjusted odds ratio (AOR) and 95% CI estimates of the effect of LNS supplementation on malnutrition

Variable	IFA	MMN	LNS	P-value	Test
	(n)	(n)	(n)	(n)	
Percentage underweight (WAZ < -2) [% (95% CI)]	x.x (x.x - x.x)	x.x (x.x - x.x)	x.x (x.x - x.x)	x.xx	FREQ
AOR (95% CI)	x.x (x.x - x.x)	x.x (x.x - x.x)			Logistic regression
Percentage stunted (LAZ < -2) [% (95% CI)]	x.x (x.x - x.x)	x.x (x.x - x.x)	x.x (x.x - x.x)	x.xx	FREQ
	x.x (x.x - x.x)	x.x (x.x - x.x)			Logistic regression
Percentage wasted (WLZ < -2) [% (95% CI)]	x.x (x.x - x.x)	x.x (x.x - x.x)	x.x (x.x - x.x)	x.xx	FREQ
AOR (95% CI)	x.x (x.x - x.x)	x.x (x.x - x.x)			Logistic regression
Percentage severely underweight (WAZ < -3) [% (95% CI)]	x.x (x.x - x.x)	x.x (x.x - x.x)	x.x (x.x - x.x)	x.xx	FREQ
AOR (95% CI)	x.x (x.x - x.x)	x.x (x.x - x.x)			Logistic regression
Percentage severely stunted (LAZ < -3) [% (95% CI)]	x.x (x.x - x.x)	x.x (x.x - x.x)	x.x (x.x - x.x)	x.xx	FREQ
AOR (95% CI)	x.x (x.x - x.x)	x.x (x.x - x.x)			Logistic regression
Percentage severely wasted (WLZ < -3) [% (95% CI)]	x.x (x.x - x.x)	x.x (x.x - x.x)	x.x (x.x - x.x)	x.xx	FREQ
AOR (95% CI)	x.x (x.x - x.x)	x.x (x.x - x.x)			Logistic regression

List of figures

Figure 1 Participant flow chart.
